13.5.3 Analysis of Secondary Endpoints

13.5.3.1 Safety

The analysis of secondary safety endpoints will be performed using the safety population.

The percentage change from Baseline in hip bone mineral density measured in g/cm² by DEXA will be summarised by treatment arm and visit. A single sample 1-sided t-test conducted at the 2.5% significance level will be used to analysis percentage change from Baseline (MBGS205) at Week 48 (MBGS206) in each treatment arm to test the null hypothesis that the percentage decrease from Baseline is $\leq 3\%$. Only subjects that have a post-Baseline DEXA assessment in MBGS206 will be included in this analysis.

The percentage change from Baseline in bone turnover markers, bone density, bone biomarkers and oestradiol (absolute and percentage) will be summarised by treatment arm and visit. A 95% CI will be presented for the mean change at each visit.

The proportion of subject with a T-score ≤ -2.5 at Week 48 will be summarised by treatment arm and visit. A 95% CI will be presented for the proportion of subjects with a T-score ≤ -2.5 .

The proportion of subjects with testosterone ≤ 1000 ng/dl (35 nmol/L) and > 1000 ng/dl (35 nmol/L) will be summarised by treatment arm and visit.

TEAEs will be summarised per [Section 13.5.5](#). For subjects randomised to active treatment in Study MBGS205 first dose is considered as the first dose in Study MBGS205. For subjects randomised to placebo in Study MBGS205 first dose is considered as the first dose in Study MBGS206.

A more detailed description will be presented in the SAP.

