13.5.3.2 Efficacy

The analysis of the secondary efficacy endpoints will be performed using the ITT population.

The proportion of subjects that have normalisation of testosterone at Week 48 will be summarised by treatment arm and visit. For each treatment arm an exact 2-sided binomial test conducted at the 5% significance level will be performed to test the null hypothesis that the proportion of normalised subjects is $\leq 75\%$. An alternative way of expressing this is that the null hypothesis will be rejected for a treatment group and the endpoint considered met if the lower bound of the 2-sided 95% CI for the proportion of subjects with testosterone normalisation is greater than 75%.

The change from Baseline in total and bioavailable testosterone, LH, and FSH will be summarised by treatment arm and visit. A single sample 2-sided t-test conducted at the 5% significance level will be used to analyse the percentage change from Baseline at Week 48 within each treatment arm.

For subjects randomised to placebo in Study MBGS205, unless otherwise stated, the Extension Study Baseline (Week 24) will be used for analysis of efficacy endpoints to Week 48.

A more detailed description will be presented in the SAP.

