#### 8.1.1 Populations for analysis

Demographic and baseline characteristics will be summarised by Safety, Completers and ITT populations, unless otherwise stated.

Analyses of the primary endpoint and secondary safety BMD endpoints will be performed on ITT and completer population. Analysis of all other safety endpoints will use the safety population.

The secondary efficacy endpoints and exploratory endpoints will be analysed using the ITT population.

The safety and tolerability variables will be analysed using the Safety population.

PK data will be analysed using the PK population.

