#### 8.6.2 Analysis of primary endpoint

The Primary Endpoint is defined as the change in lumbar bone density measured by DEXA from baseline in Study MBGS205 to Week 48 in Study MBGS206 by dose group in subjects randomised to active treatment in Study MBGS205.

DXA Scan assessments will only be performed at the EOT visit (for subjects that reached at least Week 36) and will be over-read by IMI. The DEXA over-read data will be used for the primary endpoint statistical analysis.

Descriptive statistics (observed values, changes from baseline and percentage change from baseline) in lumbar bone mineral density will be presented for each treatment regimen and time-point. A single sample 1-sided t-test conducted at the 2.5% significance level will be used to analyse percentage change from Baseline (MBGS205) to Week 48 (MBGS206) LOCF in each treatment arm to test the null hypothesis that the percentage decrease from Baseline is  $\leq 3\%$ . P-values and associated CI will be presented.

Only subjects included in the safety population that have a post-Baseline DEXA assessment in MBGS206 and were randomised to active treatment in Study MBGS205 will be included in this analysis. The analysis will be repeated for subjects included in the completer population.

Observed and percentage change from baseline values at each visit will be presented in a line graph by treatment group.

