#### 8.6.3.1 Testosterone Normalisation (Primary Definition)

The number and proportion of subjects with normal testosterone levels (testosterone value is between 300-1000 ng/dL inclusive) will be summarised by treatment regimen at each visit using the total testosterone assessed by ICON central lab. Observed values and LOCF values will be presented. In addition, a P-value for the comparison between each dose will be provided using Fisher's exact test.

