### 8.8.4 Sensitivity Analysis of Site 1156

To assess the impact of site 1156 on key endpoints the below analyses will be conducted utilising the modified populations (see section 6.0) which removes subjects enrolled from site 1156:

- Analysis of Proportion of Subject Achieving Normalisation of Total Testosterone (300-1000 ng/dl). Analysis will be conducted on the Central lab testosterone using LOCF imputation.
- Summary of Change in LH and FSH
- Summary of Vitals signs Parameters and Change from Baseline
- Summary of Blood Pressure Categorisation
- Summary of Body Composition

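### The SAP drops the protocol's per-arm 75% normalisation test and 3% hip BMD test without declaring it, and leaves two retained bone endpoints without an adequate analysis

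*SAP*

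**What the plan says.** **Normalisation.** Protocol 13.5.3.2 states that for each arm "an exact 2-sided binomial test conducted at the 5% significance level will be performed to test the null hypothesis" that the normalised proportion is at most 75%. It then adds: "An alternative way of expressing this is that the null hypothesis will be rejected for a treatment group" when the lower limit of the two-sided 95% confidence interval is above 75%. SAP 8.6.3.1 has proportions (observed and LOCF), and "a P-value for the comparison between each dose will be provided using" Fisher's exact test. SAP 8.6.1 also offers only Fisher for binary outcomes.

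**Hip BMD.** Under Protocol 13.5.3.1 a one-sample, one-sided 2.5% t-test "will be used to analysis percentage change from Baseline" at the hip in each arm, with the null that the loss is at most 3%. SAP 8.6.2 keeps this form for lumbar BMD only, using Week 48 "LOCF in each treatment arm to test the null hypothesis that the percentage decrease from Baseline is" at most 3%. SAP 8.7.1 gives the hip descriptive statistics, an MMRM for continuous-active subjects and an ANCOVA for placebo-switch subjects.

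**T-score.** SAP 4.2.1 keeps the proportion with T-score ≤ -2.5 at Week 48, and Protocol 13.5.3.1 requires a 95% interval for it. SAP 8.7.1 plans T-score descriptives and a severity shift table.

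**BMD and hormones.** SAP 2.4 and 4.2.1 keep the relationship of BMD change to Week 48 oestradiol and total testosterone. SAP 8.8.3, which lists the association analyses, does not mention BMD.

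**Declared changes.** SAP section 9 has three entries: an added lumbar endpoint for placebo-switch subjects, the vitamin D cut-off, and the site 1156 sensitivity analyses.

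**The concern.** The protocol set a pass/fail criterion per dose for two secondary endpoints. A between-dose comparison answers a different question: whether doses differ, not whether any dose clears 75% or loses more than 3%. A team following the SAP as written would report no verdict on either criterion, and a reader of section 9 would not learn that they had gone. The study's main purpose is bone safety, yet one bone objective has no planned analysis and one bone endpoint has no planned interval.

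Traceability matters a little more than usual here. Protocol 10.2.4 and SAP 3.2.3 have the sponsor and CRO unblinded to MBGS206 when MBGS205 is unblinded.

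**Working it through.** The documents give no sample-size figure for these tests, so there is none to reproduce. Arm sizes follow the protocol synopsis: 30 entered per dose and about 17% dropout, so 30 × 0.83 = 24.9, or about 25 completing.

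**1. Side by side**

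| Item | Protocol | SAP analysis | In SAP 9? |
|---|---|---|---|
| Normalisation | Per-arm exact test against 75% | Proportions; Fisher between doses | No |
| Hip BMD | Per-arm one-sided 2.5% test against 3% | Descriptives, MMRM, ANCOVA | No |
| T-score ≤ -2.5 | Proportion with 95% CI | T-score descriptives; shift table | No |
| BMD and hormones | Endpoint, no method given | None | Not applicable |

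**2. Normalisation.** The Clopper-Pearson lower limit L solves P(X ≥ x; n, L) = 0.025. L exceeds 75% exactly when P(X ≥ x; n, 0.75) is below 0.025.

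| Result | Tail at 75% | Lower limit | Above 75%? |
|---|---|---|---|
| 28/30 (93.3%) | 0.0106 | 77.9% | Yes |
| 27/30 (90.0%) | 0.0374 | 73.5% | No |
| 24/25 (96.0%) | 0.0070 | 79.6% | Yes |
| 23/25 (92.0%) | 0.0321 | 74.0% | No |

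Fisher for 28/30 against 27/30 gives p = 1.00, although the two arms fall on opposite sides of the rule. Conversely, 15/25 against 15/25 and 24/25 against 24/25 both give p = 1.00, with lower limits of 38.7% and 79.6%. A bare proportion of 92% would look comfortably above 75%, yet it fails the protocol's rule at n = 25.

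**3. Hip BMD.** The dropped statistic is t = (mean loss − 3)/(SD/√n). The documents give no SD of percentage change, so assume 2% to 5%, with n = 25 and a mean loss of 5.5%. At SD 2%, t = 2.5/0.4 = 6.25. At SD 5%, t = 2.5/1.0 = 2.50, one-sided p = 0.0098 on 24 df. The 3% null is rejected throughout that range. If two doses both lost 5.5%, their difference would be zero, so the MMRM contrast would not address the criterion.

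**4. T-score.** With 0/25 the exact upper limit is 1 − 0.025^(1/25) = 13.7%. With 1/25 (4.0%) the interval is 0.1% to 20.4%. A low count therefore says little without its interval. Nor can the endpoint be read from the shift table. SAP 7.1.4.4 defines osteoporosis as T < -2.5, or Z < -2.0 under age 50. T = -2.5 exactly meets the endpoint but not the T-score part of that class. A man under 50 with T = -2.3 and Z = -2.1 falls in both osteopenia and osteoporosis.

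**5. BMD and hormones.** SAP 8.8.3 has 7 + 7 + 4 = 18 bullets, and none names BMD. Blood pressure against the same Week 48 hormones is listed.

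**The case against.** All analyses are labelled exploratory, with no multiplicity adjustment (Protocol 13.5.1, SAP 8.6.1.1), and the protocol defers detail to the SAP. The table shells are a separate document (SAP section 1), and SAP 8.1.4 promises intervals where relevant. A reader can rebuild the 75% result from the counts and the hip result from n, mean and SD. The per-arm least-squares means would also make a large hip loss visible.

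Most of this stands and limits the consequence. It does not supply the missing 75% and 3% nulls or the BMD-hormone analysis. Deferring detail is also not the same as dropping a stated test without declaring it.

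On the T-score, osteoporosis by DEXA (T ≤ -2.5) is an adverse event of special interest (Protocol 12.1.7), and SAP 8.7.4 tabulates such events by number and percentage of subjects. A reader might infer that this endpoint gets no planned result at all, and that would be too strong. The event table covers it partly, but it has no interval and depends on event reporting.

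A reader might also infer that the protocol's exact test and its interval rule contradict each other. For 24/26 a minimum-likelihood two-sided p is 0.041, while the lower limit is 74.9%. The protocol does not name that p-value. The doubled-tail exact p, which matches Clopper-Pearson, is 0.052 and agrees with the interval. The documents do not show a contradiction.

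**Conclusion.** The point holds and should be corrected. Two protocol tests are absent from the SAP and from its list of changes, one retained bone objective has no analysis, and one retained bone endpoint lacks a dedicated table and its required interval.

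The damage is limited to the planned verdict on the protocol's own criteria, traceability, and completeness of the bone-safety reporting. The primary lumbar test, sample size and conduct are untouched.

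Three further inferences go beyond the documents. The BMD-hormone omission is a gap, not a departure, because the protocol gave no method. Nothing shows that the omissions were deliberate or made with knowledge of results. Nor does LOCF become the main analysis of normalisation because SAP 8.8.4 says "Analysis will be conducted on the Central lab testosterone using LOCF imputation". That sentence governs a site sensitivity analysis, while Protocol 13.5.1 and SAP 7.2.1 default to observed cases.

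The binomial results depend only on the counts and the 75% threshold. The hip illustration rests on an assumed mean loss and SD range. The shells were not available.

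**What to change.** - **SAP 8.6.3.1.** Add, per dose at Week 48, the Clopper-Pearson 95% interval with the rule that the lower limit exceeds 75%. Define any exact p to match that interval. Show observed cases, with LOCF as already planned. Use the protocol's efficacy-based ITT (13.3.1). The SAP's ITT (6.1) requires an MBGS206 lumbar scan, which subjects stopping before Week 36 do not get, so it would remove them from a testosterone analysis.
- **SAP 8.7.1, hip.** Add the one-sample, one-sided 2.5% test of loss ≤ 3% with its interval, for total hip and femoral neck in continuous-active subjects. Use the same over-read data and analysis set as the lumbar test. First reconcile that set: SAP 8.1.1 says "Analyses of the primary endpoint and secondary safety BMD endpoints will be performed on ITT and completer population", while 8.6.2 says "Only subjects included in the safety population that have a post-Baseline DEXA assessment in MBGS206", repeated in completers.
- **T-score.** Tabulate the Week 48 proportion ≤ -2.5 by dose with an exact 95% interval. In 7.1.4.4 make the T-score classes mutually exclusive and consistent with the endpoint's ≤ -2.5, and show the under-50 Z-score category separately.
- **SAP 8.8.3.** Add one pre-specified correlation and regression of percentage change in lumbar BMD (hip as supportive) on Week 48 oestradiol and total testosterone. Fit it in continuous-active subjects, pooled, with dose group as a covariate.
- **SAP section 9.** Declare and justify any protocol analysis that stays dropped.

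The cost is SAP wording and a few extra tables from data already collected.

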#### 8.6.3.2 Testosterone Normalisation (Secondary Definition)

The secondary definition of testosterone normalisation (350-1170 ng/dL inclusive) that allows a decrease in total testosterone due to diurnal variation will be analysed in the same manner as primary definition of testosterone normalisation.

#### 8.6.3.3 Change from Baseline in Total Testosterone

A descriptive summary table will be presented for Total Testosterone values and percentage change from baseline in Total Testosterone values by treatment regimen and visit using both ICON central lab assessed testosterone.

A single sample 2-sided t-test conducted at the 5% significance level will be used to analyse the percentage change from Baseline at Week 48 within each treatment arm. The p-value and associated confidence interval will be presented.

In addition the percentage change from baseline in Total Testosterone up to Week 48 for subjects randomised to active in Study MBGS206 using the ICON central lab assessed values will be analysed using an MMRM model as described in Section 8.6.1. Least squares means and standard

errors will be presented for each visit, p-value and 2-sided 95% confidence interval for treatment differences will be presented for each visit. Significance tests will be based on least-squares means using a two-sided  $\alpha = .05$ .

A figure presenting the least square mean change from baseline in total testosterone at each visit by treatment regimen will also be provided.

The above analyses will be repeated for subjects that were randomised to placebo in Study MBGS205 by analysing the change from MBGS206 baseline (Week 24) to Week 48.

### 8.6.3.4 Proportion of subjects that Overshoot Testosterone

The number and proportion of subjects that overshoot testosterone (total testosterone above 1000 ng/dL [35 nmol/L]) at each visit and at least once during the study will be summarised similar to that of Testosterone normalisation.

In addition the number and proportion of subjects whose maximum testosterone value falls into each of the below categories will be presented by visit and overall during the study:

- >1000 - <=1500ng/dl
- >1500 – <1800 ng/dL
- =>1800 - <= 2500 ng/dL
- >2500 ng/dL

### 8.6.3.5 Change from Baseline in Free and Bioavailable Testosterone

Descriptive summary tables will be presented for Free and Bioavailable Testosterone values and change from baseline in Free and Bioavailable Testosterone by treatment regimen and visit.

The change from baseline in Free and Bioavailable Testosterone will be analysed in the same manner as the change from baseline in total testosterone for subjects that were randomised to active treatment in study MBGS205 (see Section 8.6.3.3). For subjects that were randomised to placebo in study MBGS205, the change from baseline will be analysed using an ANCOVA model with treatment as a fixed effect and baseline value as a covariate. Least squares means and standard errors will be presented for each visit, p-value and 2-sided 95% confidence interval for treatment differences across all doses will be presented for each visit. Significance tests will be based on least-squares means using a two-sided  $\alpha = .05$ .

### 8.6.3.6 Change in LH and FSH

Descriptive summary tables will be presented for LH and FSH values and change from baseline in LH and FSH by treatment regimen and visit.

The change from baseline in LH and FSH up to Week 48 will be analysed in the same manner as the change from baseline in bioavailable testosterone (see Section 8.6.3.5). Analyses will be conducted separately for subjects that were randomised to active treatment (MMRM analysis) and subjects that were randomised to placebo (ANCOVA analysis) in study MBGS205.

A figure presenting the least square mean change from baseline in LH and FSH at each visit by treatment regimen will also be provided.

#### 8.6.4 Analysis of exploratory endpoint(s)

The analysis of exploratory endpoints will be performed on the ITT population.

##### 8.6.4.1 Change in Body composition

Descriptive summary tables will be presented for Body Weight, BMI, Waist Measurement, Hip Measurement and Waist to Hip Ratio values and change from baseline values by treatment regimen and visit.

The number and proportion of subjects with gynecomastia will be summarised by treatment regimen at each visit. A P-value for the comparison of the presence of gynecomastia between each dose of BGS649 and placebo will be provided using Fisher's exact test. A descriptive summary table for the size of glandular breast tissue will be presented for those subjects with gynecomastia.

The change from baseline in each parameter up to Week 48 will be analysed via t-test and MMRM in the same manner as the change from baseline in total testosterone (see Section 8.6.3.3). Analyses will be conducted separately for subjects that were randomised to active treatment and subjects that were randomised to placebo treatment in study MBGS205.

Descriptive summary tables will be presented for all body composition bio impedance parameters [Total Fat (kg and percentage), Visceral adipose tissue, Total fat free mass (kg and percentage) and Skeletal muscle mass whole body, right arm, right leg, left arm, left leg and torso] values and change from baseline values by treatment regimen and visit.

The change from baseline in each parameter up to Week 48 will be analysed via t-test and MMRM in the same manner as the change from baseline in total testosterone (see Section 8.6.3.3). Analyses will be conducted separately for subjects that were randomised to active treatment and subjects that were randomised to placebo treatment in study MBGS205.

A subgroup analysis of body composition parameters by baseline total testosterone (<200ng/dL vs >=200ng/dL) as assessed by ICON central labs will be conducted. Descriptive summaries and analysis up to Week 48 as described above will be presented.

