
Name of Sponsor/Company: Mereo BioPharma 2 Ltd	Individual Study Table Referring to Part of the Dossier:	(For National Authority Use Only)
Name of Product: BGS649		
Name of Active Ingredient: 4,4'-[fluoro-(1-H-1,2,4-triazol-1-yl)methylene]bisbenzotrile	Volume: Page:	
Test Product, Dose and Mode of Administration: BGS649 is prepared [REDACTED] [REDACTED] Subjects will receive [REDACTED] [REDACTED]		
Reference Therapy, Dose and Duration of Administration: None.		
Duration of Treatment in Study MBG206: Subjects will be treated for maximum of 24 weeks with BGS649, with a 12 week follow-up period after completion		

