10.2.2 Labelling

Labels will comply with the legal requirements of each country and be printed in the local language. They will supply no information about the subjects. Packs are labelled for both MBGS205 and MBGS206. However, the IRT will not allow allocation of placebo packs to subjects in MBGS206.

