## 3 STUDY DESIGN

### 3.1 General study design

This is a 6 month, active treatment, extension study, open to subjects who have completed the full 24 week treatment period in Study MBGS205 (a Phase IIb multicentre, double-blind, dose-ranging, randomised, placebo-controlled study evaluating safety and efficacy of BGS649 in male obese subjects with HH).

Study participation will comprise of the Extension Study Baseline visit (Week 24 of Study MBGS205, where the Extension Study Baseline assessment will be performed on a same day as the EOT visit of Study MBGS205), 7 visits during the treatment period up to Week 48 (End of Treatment [EOT]), and a Follow-Up (FU) visit for safety performed at Week 60, 12 weeks after the Week 48/EOT visit.

[figure not shown]
During the 24 week treatment period, subjects will take the required [REDACTED] time schedule of regular planned dose), starting with the first dose being taken at the baseline visit. The capsules will be taken orally by the subject with water. Subjects receiving active doses of BGS649 in Study MBGS205 will continue with the same dose in Study MBGS206; this transfer will be handled by the interactive response technology (IRT) and the blind will be maintained. Subjects receiving placebo in Study MBGS205 will be re-randomised on a 1:1:1 basis to each of the active treatment arms:

- o BGS649 [REDACTED] capsules)
- o BGS649 [REDACTED]
- o BGS649 [REDACTED] capsules).

The planned interim analysis of MBGS205 determined that all active doses met efficacy and safety criteria and therefore all three doses [REDACTED] were progressed into MBGS206.

Enrolment will continue until 30 subjects from each of the previous active treatment arms in Study MBGS205 have entered this study.

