#### 8.1.2 Treatment groups

Statistics will be displayed for the following treatment regimens in the below order:

- BGS649 [REDACTED]
- BGS649 [REDACTED]
- BGS649 [REDACTED]
- Active Total (Includes all continuous active groups where applicable)
- Placebo -> BGS649 [REDACTED]
- Placebo -> BGS649 [REDACTED]
- Placebo -> BGS649 [REDACTED]
- Plabebo-> Active Total (Includes all Placebo-> Active Groups where applicable)
- Overall Total (Includes all groups where applicable)

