#### 8.6.1 Analysis methods

For binary outcomes the proportion of subjects with a response will be summarised and compared between treatment regimens using Fisher's Exact Test.

For continuous parameters, the change from baseline will be summarised by treatment arm and visit. A single sample 2-sided t-test conducted at the 5% significance level will be used to analyse the change from baseline to Week 48 within each treatment arm. In addition, the change from baseline will be assessed with a mixed model repeated measure (MMRM) analysis. Analyses will include the fixed, categorical effects of treatment, visit, and treatment-by-visit interaction, as well as the continuous, fixed covariates of the associated baseline value and baseline-by-visit interaction. An unstructured covariance matrix will be used to model the within-subject errors. If the model with the unstructured covariance matrix fails to converge, other covariance structures, including Toeplitz, compound symmetry, and spatial power, will be considered. The denominator degrees of freedom will be calculated according to the Kenward-Roger method. Significance tests for treatment differences will be based on least-squares means.

Associations between changes in PROs and changes in body composition, physical activity, sleep, and grip strength will be assessed with correlation coefficients and with separate linear regression models in which changes in PRO measure total or subscale scores will be taken as the predictor variable, and baseline score as a covariate. The associations between changes in testosterone and changes in PROs, body composition, physical activity, grip strength, and sleep will be assessed in the same way. Correlation coefficients, Beta coefficients, standard errors, and 95% CIs will be presented.

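### SAP 8.6.4.1 tests gynaecomastia for each dose against placebo, but no placebo group exists at the post-baseline breast examinations (Weeks 36 and 48)

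*SAP*

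**What the plan says.** SAP 8.6.4.1 (Change in Body composition) plans a descriptive summary and a test for gynaecomastia. The summary reads: "The number and proportion of subjects with gynecomastia will be summarised by treatment regimen at each visit". The test reads: "A P-value for the comparison of the presence of gynecomastia between each dose of BGS649 and placebo will be provided using" Fisher's exact test.

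The design sections describe a study in which nobody receives placebo:

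- Protocol synopsis: "Reference Therapy, Dose and Duration of Administration: None".
- SAP 3.1: "Subjects receiving placebo in Study MBGS205 will be re-randomised on a 1:1:1 basis to each of the active treatment arms".
- Protocol 10.2.2: "the IRT will not allow allocation of placebo packs to subjects in MBGS206".
- SAP 8.1.2 lists three continuous-dose groups, three groups that switched from placebo to a BGS649 dose, and totals. One of the totals is "Plabebo-> Active Total (Includes all Placebo-> Active Groups where applicable". No regimen is placebo alone.

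The general method for binary outcomes is in SAP 8.6.1: "For binary outcomes the proportion of subjects with a response will be summarised and compared between treatment regimens using" Fisher's exact test. Protocol 13.5.4 gives the same rule. SAP 8.6.3.1 tests testosterone normalisation, a parallel binary endpoint, between doses. SAP 8.6 requires men randomised to active and men randomised to placebo in MBGS205 to be analysed separately.

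**The concern.** A prespecified test needs two groups that exist at the visit being tested. Here the sentence names a comparator that the extension does not contain, so a programmer cannot carry it out as written at the MBGS206 examinations. Someone would then have to choose between dropping the test, comparing doses, using the switched men as the reference, or going back to MBGS205 data. SAP 3.2.3 has sponsor and CRO personnel unblinded when MBGS205 is unblinded, so that choice could be made with treatment known.

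If the switched men were used as the reference, the p-value would describe a difference in length of active exposure rather than a difference from placebo. A reader guided by the SAP sentence could then take a non-significant result as no excess over placebo.

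**Working it through.** The plan gives no figure to reproduce on this point. The check sets the sections side by side and counts the groups.

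**1. When is gynaecomastia assessed in MBGS206?** Breast examination is part of the full physical examination (Protocol Table 9–1). SAP 8.7.7 places that examination at Weeks 36 and 48. The Week 24 result is transferred from MBGS205.

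**2. Which regimens exist at Weeks 36 and 48?** SAP 8.1.2, leaving out totals: 3 continuous doses + 3 switched groups = 6 regimens, of which 0 are placebo. Dose-versus-placebo comparisons available at either visit: 0.

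**3. What would the switched men represent as a reference?** Exposure is counted from each cohort's first BGS649 dose, using the documents' own convention that 24 weeks is 6 months (4 weeks per month).

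| Visit | Continuous active | Switched from placebo |
|---|---|---|
| Week 36 | 36 weeks = 9 months | 36 − 24 = 12 weeks = 3 months |
| Week 48 | 48 weeks = 12 months | 48 − 24 = 24 weeks = 6 months |

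Both columns are active treatment. Comparing across them also breaks the separate-cohort rule in SAP 8.6.

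**4. Is there a true placebo contrast anywhere?** Yes, at Week 24. SAP 8.1.5 sets baseline for the switched men as the last value before their first MBGS206 dose, so their Week 24 examination still reflects placebo. A contrast there would cover only men who entered the extension, would cross the two cohorts, and would concern MBGS205 treatment.

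**5. Does the SAP declare a departure from the protocol?** No. SAP section 9 lists three changes: an added lumbar density endpoint for switched men, a vitamin D cut-off, and the site 1156 sensitivity analyses. None introduces a placebo comparison, so the rule in Protocol 13.5.4 has not been knowingly replaced.

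**6. What does the general rule give instead?** Three doses give 3 × 2 / 2 = 3 pairs in each cohort. At each post-baseline visit tested, that is 3 comparisons among continuous men and 3 among switched men.

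**7. How would a test against switched men behave?** The documents fix no number of switched men, so the sizes and rates here are assumptions: 25 to 30 men per continuous dose, 8 to 10 per switched dose, and Fisher's exact test, two-sided at 5%. Power was computed by summing binomial probabilities over every outcome with p ≤ 0.05, for 25 v 8, 28 v 9 and 30 v 10.

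| True rate, continuous v switched | Power |
|---|---|
| 10% v 10% | 1.3 to 1.7% |
| 10% v 30% | 23 to 27% |
| 30% v 10% | 5 to 15% |
| 10% v 50% | 62 to 69% |
| 50% v 10% | 47 to 58% |

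**The case against.** The strongest reply is that the correct method is already in the plan. SAP 8.6.1 and Protocol 13.5.4 set the binary rule, SAP 8.6 separates the cohorts, and SAP 8.6.3.1 words a parallel endpoint correctly. On that view this is a stray phrase, and a programmer who found no placebo column would probably raise a query. This stands as a limit on the consequence. It does not remove the conflict, because the specific sentence in 8.6.4.1 would ordinarily be read as overriding the general one.

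The outcome is also minor. Gynaecomastia is listed among the assessments in Protocol 11.1 but is not named in the exploratory endpoint lists (Protocol 13.4.2.4, SAP 4.3). All analyses are exploratory without multiplicity adjustment. The descriptive counts are sound as planned. All of this stands.

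Three stronger readings are tempting, and the documents do not support them:

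- **That no placebo contrast is possible at all.** The Week 24 examination provides one, although not one that bears on MBGS206 treatment.
- **That a test against the switched men would almost never reach significance.** This holds when the true rates are close. With large differences, the assumed arm sizes give power above 60% in one direction and around half in the other. Low power also does not separate the error from its remedy: dose-versus-dose tests among switched men (9 v 9, assumed) have about 5% power for 10% v 30% and 30% for 10% v 50%.
- **That a mislabelled table will appear.** The column labels in SAP 8.1.2 show that switched men are on BGS649, so mislabelling is only a possibility.

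The number of p-values affected is also not fixed. The SAP attaches the by-visit wording to the summary and does not say at which visits the p-value is wanted.

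**Conclusion.** The sentence is wrong as written. At Weeks 36 and 48 there are no placebo subjects, so none of the three dose-versus-placebo tests can be formed at either visit. The nearest substitute compares about 9 with 3 months, or 12 with 6 months, of active exposure and conflicts with SAP 8.6. This conclusion rests only on the design, the regimen list and the examination schedule. It needs no assumption about event rates or arm sizes.

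The consequence is small: one exploratory outcome, with the primary lumbar bone density analysis unaffected. It is worth correcting because the correction changes which test is run and costs almost nothing.

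**What to change.** In SAP 8.6.4.1, replace the comparison of each dose with placebo by pairwise comparisons between the BGS649 doses using Fisher's exact test, done separately for men randomised to active and men randomised to placebo in MBGS205. State whether the p-value is wanted at Week 36, Week 48 or both.

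This agrees with SAP 8.6, 8.6.1 and 8.6.3.1 and with Protocol 13.5.4, so it restores the protocol's method. If dose comparisons among the few switched men are thought uninformative, the p-value can be dropped there and the planned descriptive summary kept.

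The cost is one phrase in the SAP and the matching table shell. No new data, sample size or protocol change is needed.
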